5.5.9 Laboratory Data

For the laboratory values, if the value is below the lower limit of quantification, half of the lower limit will be used for quantitative summaries. If the value is above the upper limit of quantification, the upper limit value will be used. If more than one laboratory value is reported for the same visit, the latest value will be used in summary statistics and analyses.

If laboratory parameters are missing for a subject at baseline or at randomisation the change from baseline or randomisation to a specific visit will not be calculated.

Laboratory parameters will be categorised as described in the protocol.

Open-label phase:

The change in each of the laboratory parameters from baseline to end of open-label treatment phase will be summarised. A shift table for categories of laboratory parameters at visit 1 versus the category at visit 2 will also be done.

Maintenance phase:

The change in laboratory parameters from randomisation to end of maintenance phase for subjects discontinuing before 6 months after randomisation, the change in laboratory parameters from randomisation to end of maintenance phase for subjects discontinuing on or after 6 months after randomisation, and the change in laboratory parameters from randomisation to visit 15 will be summarised.

Trial ID: LP0053-1004	Date: 15-JUL-2019	Version: 1.0 Page 37 of 177
-----------------------	-------------------	--------------------------------

Shift tables showing the categories at randomisation against those at end of maintenance phase for subjects discontinuing before 6 months after randomisation, for subjects discontinuing the trial on or after 6 months after randomisation, and for subjects completing the maintenance phase will be produced.

For subjects with at least one clinically significant value of albumin corrected serum calcium, similar shift tables as described above will be produced.

All laboratory data will be listed. Additionally, subjects with laboratory parameters outside the reference range will be listed in a separate listing.

Further details for the tables and listings can be found in [Appendix I](#) and [Appendix II](#).

5.6 General Principles

5.6.1 Pooling of Trial Sites

As many centres randomises only a few subjects, the centres will be pooled together. For the United States, due to the large geographical area and diverse climatic conditions, centres will be pooled with neighbouring centres based on graphical location and climatic zones to form two pooled centres. The pooling of sites is shown in [Table 8](#).

Table 8: Pooling of trial sites

Country	Number of subjects randomised	Pooled sites
Canada	132	CAN140, CAN142, CAN143, CAN144, CAN145, CAN146, CAN147, CAN148, CAN149, CAN150, CAN152, CAN154
France	55	FRA160, FRA161, FRA162, FRA165, FRA167
Germany	52	DEU183, DEU185, DEU186, DEU187, DEU188, DEU189, DEU193
Great Britain	68	GBR200, GBR201, GBR202, GBR203, GBR207, GBR209, GBR210

Poland	56	POL220, POL221, POL222, POL224
United States (1)	68	USA103, USA106, USA109, USA112, USA122
United States (2)	114	USA100, USA102, USA104, USA107, USA108, USA110, USA111, USA113, USA115, USA116, USA117, USA118, USA119, USA120, USA121

5.6.2 Handling of Drop-outs and Missing Values

The methods of dealing with drop-outs and missing values for primary and secondary endpoints are specified in the relevant sections of the statistical analysis plan, where the analyses of the endpoints are described. If nothing is specified in these sections, missing data and drop-outs are not an issue of concern for the analyses of the endpoint and nothing will be done.

5.6.3 Incomplete dates

For incomplete start dates of adverse events in data, the following rules apply:

[figure not shown]
- If a start day is missing, but start month and year is not missing, it will be assumed that the start date of the adverse event is the date of last contact with the subject in that month, if available, and otherwise it will be the first day of the month.
- If both start day and month is missing, it will be assumed that the start date of the adverse event is the date of the last contact with the subject before the end date of the adverse event.

The adverse events will be assigned to rescue medication and randomised treatment as described in section [5.5.3](#) based on the imputed dates derived from the above rules.

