5.1 Definition of trial periods

The trial periods are defined in [Table 1](#).

Table 1: Definition of trial periods

Trial period	Definition
Open-label phase	From the day of enrolment to the day before randomisation.
Randomised phase	From the day of randomisation to end of trial, both days included.
Maintenance phase	From the day of first exposure to maintenance IMP to the last day of exposure (rescue or maintenance IMP), both days included.
Follow-up phase	From the day after last application of maintenance or rescue IMP to end of trial.
Relapse period	Relapse is defined as a PGA score of at least 'mild' during the maintenance phase, for details on relapse see CTP section 6.14.1. A relapse period is defined from the relapse start day (included) to the

	visit date when relapse treatment is discontinued (not included).
Remission period	A remission period is a period where the subject is not in a relapse period within the maintenance phase.
Visit interval	The interval between two successive scheduled visits.

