5.5.3 Adverse Events

The adverse events (AEs) will be assigned to a specific period (e.g. open-label phase or randomised phase) based on the onset date the AE.

The long-term safety of LEO 90100 will be evaluated based on data from the randomised phase.

For treatment emergent adverse events (hereafter referred to as AEs) occurring in the randomised phase the following tables will be done:

Trial ID: LP0053-1004	Date: 15-JUL-2019	Version: 1.0 Page 31 of 177
-----------------------	-------------------	--------------------------------

An overall summary of AEs, SAEs, premature discontinuation from the trial due to AEs, treatment related AEs, severity of AEs, action taken with IMP and outcome of AEs will be presented. The summary will include number of events, number (percentage) of subjects and exposure rates.

The number of AEs, the number and percentage of subjects experiencing each type of AE, and the exposure rate will be tabulated by SOC and preferred term. The tabulation will be done for all treatment emergent AEs, for each type of severity separately, for related AEs, for serious AEs (SAEs), for non-serious adverse events, and for frequent AEs ($\geq 1\%$ in any treatment group).

All above tables will be done for the safety analysis set by treatment for the first 28 weeks of the randomised phase, and for the remaining 32 weeks of the randomised phase separately. In addition, the tables will be done for the safety analysis set by randomised treatment and rescue IMP for the total randomised phase, for the first 28 weeks of the randomised phase, and for the remaining 32 weeks of the randomised phase separately.

Further details for the tables can be found in [Appendix I](#) and [Appendix II](#).

Open-label phase:

For completeness, AEs for the open-label phase will be summarised separately as follows:

An overall summary of AEs, SAEs, AEs leading to withdrawal, treatment related AEs, severity of AEs, action taken with IMP and outcome of AEs will be presented. The summary will include number of events, number (percentage) of subjects and exposure rates.

The number of AEs, the number and percentage of subjects experiencing each type of AE, and the exposure rate will be tabulated by SOC and preferred term. The tabulation will be done for all treatment emergent AEs, for each type of severity separately, for related AEs, for serious AEs (SAEs), for non-serious adverse events, and for frequent AEs ($\geq 1\%$).

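### SAP 5.6.3: the rule for a missing start day can date an adverse event after it ended, and it counts some open-label events in the randomised phase

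*SAP*

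**What the plan says.** SAP 5.6.3 has two rules for incomplete AE start dates. With only the day missing: "it will be assumed that the start date of the adverse event is the date of last contact with the subject in that month". Where the subject had no contact in the month, the fallback is day 1 of that month. With day and month missing, onset is "the date of the last contact with the subject before the end date of the adverse event". The second rule is therefore bounded by the stop date; the first is not.

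These dates decide which table an AE enters. Section 5.6.3 goes on, pointing to section 5.5.3 and relying on the imputed dates: "The adverse events will be assigned to rescue medication and randomised treatment as described in section". Section 5.5.3 says that AEs "will be assigned to a specific period (e.g. open-label phase or randomised phase) based on the onset date the AE", and adds: "The long-term safety of LEO 90100 will be evaluated based on data from the randomised phase".

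Table 1 in SAP 5.1 sets the boundaries. The open-label phase stops on the day before randomisation. The randomised phase is "From the day of randomisation to end of trial, both days included". For relapse the table has: "A relapse period is defined from the relapse start day (included) to the". What follows there is the visit at which relapse treatment stops, and that last day is excluded.

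**The concern.** An imputed onset should be a date on which the AE could have begun, and it should not move the AE systematically across a treatment boundary. The missing-day rule can fail on both counts.

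First, it looks at the last contact of the month even if the AE had already resolved.

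Second, if Visit 2 is the last contact in the onset month, an AE that began during once-daily open-label LEO 90100 is dated to the first day of the randomised phase. It is then counted in the phase used to judge long-term safety, and for half of the subjects in the vehicle column. The same mechanism works at visits that start or end rescue, and so affects the tables that compare remission with relapse.

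The year-only rule has two gaps of its own. It needs an end date, so it gives nothing for an ongoing AE, and it does not confine the result to the year that is known.

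**Working it through.** The plan states no figure on this point, so there is none to reproduce. The checks are examples, one hand calculation and a Monte Carlo run.

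**1. Onset after resolution.** Take a start of March (day unknown), a stop on 6 March and a last March contact on 27 March. The rule gives onset on 27 March, which is 27 − 6 = 21 days after the AE ended.

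**2. Year-only rule.** Take a start of 2017 (day and month unknown), a stop on 20 February 2018 and a last earlier contact on 5 February 2018. The rule gives an onset in 2018, outside the known year. With no stop date it gives no value.

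**3. Open-label to randomised, by hand.** Let Visit 2 fall on day d of a month, with the 28 open-label days before it and onset uniform over them. An AE moves forward if it began in the same calendar month as Visit 2, so the share is min(d − 1, 28)/28. Averaged over d:

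- 28-day month: (0 + 1 + … + 27)/(28 × 28) = 378/784 = 48%
- 30-day month: (0 + 1 + … + 28 + 28)/(30 × 28) = 434/840 = 52%
- 31-day month: (0 + 1 + … + 28 + 28 + 28)/(31 × 28) = 462/868 = 53%

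No AE moves back, because every contact in a month that contains a post-randomisation onset and falls last is Visit 2 or later.

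**4. Monte Carlo on calendar dates** (1,500 subjects per scenario). Inputs from the documents: visits every 4 weeks with a window of ±4 days, 4-week rescue, 4, 6 or 8 vehicle relapses per year (Protocol 11.1), and the SAP Table 1 boundaries. Assumptions where the documents are silent: every AE lacks only its day; onset uniform over days within a period; no withdrawals; 0% or 50% of relapses found at unscheduled visits; AE rate on rescue 1 or 2 times that in remission; exponential AE duration with mean 7, 14 or 28 days; a contact is a clinic visit or FU3. Results among AEs with a missing day:

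- Open-label AEs moved to the randomised phase: 51–53%; moved back: 0%. This agrees with step 3.
- Onset after the AE ended: 35–39% at mean duration 7 days, 25–28% at 14 days, 15–17% at 28 days.
- Vehicle remission AEs moved to relapse: 13–23%. Relapse AEs moved to remission: 43–48%.
- The contact chosen opens the randomised phase in 5–7% of AEs, opens a relapse in 15–28%, closes one in 14–28%, and is no period boundary in 37–61%.

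**5. Net effect between remission and relapse**, at 6 relapses per year with no unscheduled visits, in AEs per subject if one AE is placed on each day:

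- Equal AE rates: remission to relapse is 271.6 × 0.176 ≈ 47.9; relapse to remission is 92.4 × 0.473 ≈ 43.7. Assigned to relapse: 92.4 × 0.484 + 47.9 ≈ 92.6, so assigned/true = 92.6/92.4 ≈ 1.00.
- Rescue rate doubled: assigned to relapse is 184.1 × 0.476 + 47.6 ≈ 135.2, so assigned/true = 135.2/184.1 ≈ 0.73. Assigned/true for remission is 1.16.

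**The case against.** A reader might infer that the rule shifts vehicle AEs one way onto LEO 90100 rescue. The documents do not support that. SAP Table 1 excludes the day on which relapse treatment stops, so that visit counts as remission and rescue-period AEs move back by the same rule. The flows nearly cancel at equal AE rates, and the net error is away from rescue if rescue carries more AEs. Nor is the chosen contact usually the visit that opens the next period: that holds for about 22–35% of AEs (lowest about 7% + 15%, highest 7.0% + 27.6% = 34.6%).

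A reader might also infer that one arm is favoured. The Visit 2 shift concerns events that began before randomisation, so in expectation it adds equally to both arms. Vehicle AEs moved into relapse stay in the vehicle arm, under the Vehicle relapse column of the SAP shells. SAP 5.5.3 also drops statistical testing of AEs and presents the remission and relapse tables as additional, exploratory summaries.

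Finally, Protocol 9.2 requires a start and a stop date for each AE, Protocol 9.1 has AEs asked about at every treatment visit, and Protocol 13.2 provides for queries on discrepant data. Partial dates may be few. The last contact in the month can also precede the true onset, in which case the rule may assign the right period.

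All of this stands, and it limits the size and direction of the problem. It does not remove the impossible dates, the one-way Visit 2 shift or the undefined cases, which follow from the rules as written. One caveat: a figure placed just before the rules is not reproduced in the public text, so a bound shown there would not be visible.

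**Conclusion.** The rule is wrong as written, at minor severity. For an AE with a missing start day it can return an onset after the stop date. It also moves open-label AEs into the randomised phase, in one direction only: about half of those with a missing day, on the assumption of uniform onset and 28-day visits. The effect is to overstate the AE burden of the long-term phase in both arms, not to bias the comparison between them. Between remission and relapse the result is two-way misclassification, which blurs those tables and could dilute a rescue-related excess; totals by randomised arm over the whole randomised phase are unaffected by that part. The year-only rule is incomplete for ongoing AEs and for AEs that run across years.

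The percentages apply only to AEs with partial dates. Their number is not in the documents, so the absolute effect cannot be computed and may be small.

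**What to change.** Amend SAP 5.6.3 as follows:

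1. In both rules, cap the imputed onset at the AE stop date and keep it within the known month or year. These limits take precedence over the steps below.
2. For an ongoing AE with only the year known, use the last contact in that year, or the first day of the year if there was none.
3. Where the visit of first report can be identified, date the onset after the previous contact and before that visit. An AE first reported at Visit 2, or at a visit that starts or ends rescue, is then counted in the preceding period.
4. Otherwise, flag in the listing any AE whose possible onset window spans two periods.

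Step 1 removes onsets after resolution but does not by itself stop the Visit 2 shift. Step 3 does, because randomisation and rescue changes take place at visits; it depends on knowing when each AE was first reported, which Protocol 9.2 does not list among the items on the AE form. Simply using the first day of the month (not before Visit 1) is no substitute: in the same simulation it ends the open-label shift but moves about 5–6% of remission AEs back to open-label, 12–22% of remission AEs to relapse and 48–52% of relapse AEs to remission.

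The cost is a few sentences in the SAP, one extra derivation and a small number of flagged AEs.

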5.6.4 Multiplicity adjustment

To control the overall type 1 error rate, the analyses of the primary and secondary endpoints will follow the hierarchical testing procedure outlined in [Figure 3](#). The hypotheses relating to the two secondary endpoints cannot be rejected unless the hypothesis relating to the primary endpoint is also rejected.

Figure 3: Testing procedure for primary and secondary endpoints

The procedure will be as follows:

Time to first relapse between LEO 90100 and vehicle is evaluated at a 5% significance level. If the test is significant, the significance level will be split between the analyses of the two secondary endpoints using the Holm Bonferroni method to adjust for multiplicity. Hence the proportion of days in remission and the number of relapses during the maintenance phase between LEO 90100 and vehicle will be tested in parallel at a 2.5% significance level.

5.6.5 Treatment Labels

The treatment labels for the clinical trial report text and tables are shown in [Table 9](#).

Table 9: Treatment labels for the clinical trial report text and tables

Label Used in Text	Label Used in Tables	Order in Table
LEO 90100 aerosol foam	LEO 90100	1
LEO 90100 aerosol foam vehicle	Vehicle	2

5.7 Changes to the analyses described in the protocol

The following changes have been done to the analyses described in the protocol:

SAP section	Endpoint/Assessment	Description of change
Section 5.3.4	Compliance	
Data captured in the eDiary will not allow the computation of percentage missed application in the maintenance phase as described in the protocol (section 11.3.3.2).
 
Number of subjects in non-compliance with maintenance treatment instructions (i.e.; excluding relapse periods) will be summarised by treatment group.

Section 5.4.1	Time to first relapse (primary endpoint)	
The analysis described in the protocol includes disease severity at baseline (visit 1) as a covariate and trial site as a factor in the model (section 11.3.3.3).
 
In the SAP the disease severity at maintenance baseline and pooled sites are included in the model instead.
 
A sensitivity analysis is added in the SAP, where the primary endpoint will be analysed incorporating interval censoring. As compared to the primary analysis assuming that the start of relapse is known, the sensitivity analysis assumes the relapse starts between two visits.
 
The analysis of subjects who are still at risk for a first relapse at week 26

		and 52 mentioned in the protocol section 11.3.3.3 are described as two addition exploratory efficacy endpoints in section 5.4.3.1 .
Section 5.4.3.1	Proportion of subjects who are still at risk of a first relapse at week 26. Proportion of subjects who are still at risk of a first relapse at week 52.	These two endpoints where mentioned in section 11.3.3.3 of the protocol. In the SAP they are added as exploratory endpoints.
Section 5.4.2.1	Proportion of days in remission	Analysis of number of days in remission is described in the protocol (section 11.3.3.6). The length of the maintenance phase will vary from subject to subject and will influence the number of days in remission. Due to this reason, the endpoint in SAP has been changed to the proportion of days in remission. The imputation method described in the protocol section 11.3.3.6 is not done, since if the withdrawal rate is higher in the vehicle arm (due to lower efficacy), the approach would favour the active treatment arm. In the SAP a multiple imputation method is described instead. See section 5.4.2.1 for details.
Section 5.4.2.2	Number of relapses during the maintenance phase.	The analysis described in the protocol includes disease severity at baseline (visit 1) as a covariate and trial site as a factor in the model (section

		
11.3.3.6).
 
In the SAP the disease severity at maintenance baseline and pooled sites are included in the model instead.
 
Sensitivity analysis:
 
The analysis described in the protocol (section 11.3.3.6) will not be done as it conditions on future events by excluding subjects who at some point do not achieve 'clear' or 'almost' clear according to PGA after treatment of relapse. A negative binomial regression model will be used for the analysis instead. See section 5.4.2.2 for details.

Sections 5.4.3.2	m-PASI	
In the protocol section 11.3.4.1 it is described that the endpoint will be summarised by visit. Since per protocol subjects will be withdrawn when not achieving 'clear' or 'almost clear' according to PGA after rescue IMP, the subset of subject's available values at the visits will be a selected population (most likely are subjects who responds well to the IMP). Hence summaries by visit will not be done.
 
The summaries will be done only for data capture at the start or the end of a relapse period. See section 5.4.3.2.

Section 5.4.3.3	Physician's Global Assessments of disease severity	
This endpoint is added as compared to the protocol.
 
The summaries will be done only for data capture at the start or the end of a relapse period. See section 5.4.3.3 for details.

Section 5.4.3.5	Time to when PASI75 is no longer fulfilled	PASI and PGA are both tools for assessing the psoriasis severity and will therefore be mutually related. Since rescue IMP will be given to patients in relapse (based on the PGA) y, the level of PASI might also be affected. Therefore, the observed progress in PASI over time might be confounded with the rescue IMP. For this reason, time to when PASI75 is no longer fulfilled, will not be analysed (protocol section 11.3.4.3).
Section 5.4.3.6	Time to first relapse according to m-PASI	m-PASI and PGA are both tools for assessing the psoriasis severity and will therefore be mutually related. Since rescue IMP will be given to patients in relapse (based on the PGA) y, the level of m-PASI might also be affected. Therefore, the observed progress in m-PASI over time might be confounded with the rescue IMP. For this reason, time to first relapse according to m-PASI, will not be analysed (protocol section 11.3.4.4).
Section 5.4.3.8	Target lesion/location scores	In the protocol section 11.3.4.6 it is described that the endpoint will be summarised by visit. Since per protocol subjects will be withdrawn when not achieving 'clear' or 'almost clear' according to PGA after rescue IMP, the subset of subject's available values at the visits will be a selected population (most likely are subjects who responds well to the IMP). Hence summaries by visit will not be done. The summaries will be done only for data capture at the start or the end of a relapse period. See section 5.4.3.8 .

Section 5.4.3.9	Body surface area	
In the protocol section 11.3.4.7 it is described that the endpoint will be summarised by visit. Since per protocol subjects will be withdrawn when not achieving 'clear' or 'almost clear' according to PGA after rescue IMP, the subset of subject's available values at the visits will be a selected population (most likely are subjects who responds well to the IMP). Hence summaries by visit will not be done.
 
The summaries will be done only for data capture at the start or the end of a relapse period. See section 5.4.3.9.

Section 5.4.4.1	Total DLQI score	
In the protocol section 11.3.5.1 it is described that the endpoint will be summarised by visit. Since per protocol subjects will be withdrawn when not achieving 'clear' or 'almost clear' according to PGA after rescue IMP, the subset of subject's available values at the visits will be a selected population (most likely are subjects who responds well to the IMP). Hence summaries by visit will not be done.
 
The summaries will be done only for data capture at the start or the end of a relapse period. See section 5.4.4.1.
 
The analysis described in the protocol section 11.3.5.1 disregard the possible differences in withdrawal patterns between the two treatment groups. Instead multiple imputation for missing data and an MMRM analysis will be done. See section 5.4.4.1 for details.

Section 5.4.4.2	EQ-5D-5L PSO	
In the protocol section 11.3.5.2 it is described that the endpoint will be summarised by visit. Since per protocol subjects will be withdrawn when not achieving 'clear' or 'almost clear' according to PGA after rescue IMP, the subset of subject's available values at the visits will be a selected population (most likely are subjects who responds well to the IMP). Hence summaries by visit will not be done.
 
The summaries will be done only for data capture at the start or the end of a relapse period. See section 5.4.4.2.

Section 5.4.4.4	PSI	
In the protocol section 11.3.5.1 it is described that the endpoint will be summarised over time. Since per protocol subjects will be withdrawn when not achieving 'clear' or 'almost clear' according to PGA after rescue IMP, the subset of subject's available values over time in the trial will be a selected population (most likely are subjects who responds well to the IMP). Hence summaries over time will not be done.
 
The summaries will be done using AUC over trial phases. See section 5.4.4.4 for details.
 
The analysis described in the protocol section 11.3.5.4 disregard the possible differences in withdrawal patterns between the two treatment

		groups. Instead multiple imputation for missing data and an MMRM analysis will be done. See section 5.4.4.1 for details.
Section 5.4.4.5	SGA	
In the protocol section 11.3.5.5 it is described that the endpoint will be summarised by visit. Since per protocol subjects will be withdrawn when not achieving 'clear' or 'almost clear' according to PGA after rescue IMP, the subset of subject's available values at the visits will be a selected population (most likely are subjects who responds well to the IMP). Hence summaries by visit will not be done.
 
The summaries will be done only for data capture at the start or the end of a relapse period. See section 5.4.4.5.

Trial ID: LP0053-1004	Date: 15-JUL-2019	Version: 1.0
		Page 47 of 177

